# 4 STUDY DESIGN

### 4.1 OVERALL DESIGN

We will conduct a single-site, single-arm phase II clinical trial of NDURE among HNC patients undergoing surgery and PORT (n=45; AA n=15; white n=30). NDURE is a theory-based, multi-level PN intervention consisting of three in-person, clinic-based sessions of manualized PN with multiple intervention components that target system- (care coordination), interpersonal- (social support), and individual- (HBM; perceived susceptibility, severity, barriers, self-efficacy) level health behavior theoretical constructs to reduce barriers to care, increase HNC care delivery, and improve clinical outcomes (timely, equitable PORT). NDURE will be delivered from surgical consultation to PORT initiation (~3 months). The three in-person NDURE navigation sessions, which are expected to take 30-60 minutes each, will coincide with the presurgical consult, hospital discharge, and 1st postoperative clinic visit, time points chosen to facilitate case identification and coordination across key care transitions. Measures of PORT delay will be analyzed overall (primary outcome) and for racial differences (secondary outcome). Measures of the preliminary clinical impact of NDURE on PORT barrier reduction and delivery of key HNC care processes will be collected (secondary outcome), feasibility (secondary outcome; accrual rate, NDURE completion rate, PN caseload), acceptability (secondary outcome; satisfaction with PN). Measures of the theoretical constructs underlying the multi-level, theory-based NDURE intervention will be compared pre- and post-intervention. Post-intervention qualitative work with patients and providers will help refine NDURE.

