#### Patient and disease characteristics

- 1. Age > 18 years at the time of screening
- 2. Histologically or pathologically confirmed invasive SCC (or histologic variant) of the oral cavity, oropharynx (p16 positive, negative, or unknown), hypopharynx, larynx, unknown primary, paranasal sinuses, or nasal cavity.

a. In situations in which the patient fulfills all other inclusion criteria but the biopsy shows SCC in-situ or moderate/severe dysplasia (without definitive evidence of invasive SCC), but the patient is scheduled to undergo curative intent surgery by the treating oncologic surgeon due to clinical suspicion of invasive SCC, the diagnosis of SCC-in situ or moderate/severe dysplasia is sufficient to full the pathologic diagnosis enrollment criterion.

3. American Joint Committee on Cancer (AJCC) clinical stage grouping III-IV (8th edition) for patients with SCC of the oral cavity, p16-negative oropharynx, hypopharynx, larynx, paranasal sinuses, and nasal cavity; or AJCC clinical stage grouping III-IV (7th edition) for patients with p16-positive SCC of the oropharynx or unknown primary.

a. At screening, AJCC clinical stage grouping should be determined based on a combination of physical exam, diagnostic evaluation with cross sectional imaging of the neck (computerized tomography (CT) and/or magnetic resonance imaging (MRI)) and/or 18-F-fluoro-deoxyglucose positron emission tomography (FDG PET) CT within 30 days

b. In situations in which the patient fulfills all other inclusion criteria but the biopsy shows SCC in-situ or moderate/severe dysplasia (without definitive evidence of invasive SCC), but would otherwise have an appropriate clinical stage grouping as defined in criterion 5, the diagnosis of SCC-in situ or moderate/severe dysplasia is sufficient to full the staging enrollment criterion.

4. No prior exposure to radiation therapy, with or without concurrent chemotherapy, for treatment of HNSCC in the definitive or adjuvant therapy settings

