#### 5.2 EXCLUSION CRITERIA

An individual who meets any of the following criteria will be excluded from participation in this study:

- 1. Self-identified Hispanic ethnicity
- 2. Presence of cognitive impairment that precludes participation
- 3. Neoadjuvant immunotherapy or chemotherapy
- 4. Failure to undergo curative intent surgery at MUSC

5. Lack of indication for PORT (with or without concurrent chemotherapy) per National Comprehensive Cancer Network (NCCN) Guidelines based on the presence of at least one of the following adverse features on final pathologic evaluation: ENE, positive margin, pT3 or pT4 primary, N2 or N3 nodal disease, nodal disease in levels IV or V, PNI, or LVI

Individuals across the lifespan will be included with the following exception: children (i.e., individuals under age 18) will be excluded. Children are not eligible to participate in the study for the following scientific reasons: 1) HNSCC is a rare pediatric malignancy; and 2) the care delivery experiences of children with HNSCC are likely very different from those of adults. The age distribution included in the study (all ages >/= 18) will allow us to evaluate the feasibility and acceptability of NDURE in individuals of across the lifespan.

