#### 5.5 STRATEGIES FOR RECRUITMENT AND RETENTION

Recruitment for the single-site, single-arm, pilot trial of NDURE will occur using a clinic-based approach from the MUSC Head and Neck Tumor Center, a high-volume academic HNC program at the NCI-designated Hollings Cancer Center. Research staff will use cancer center registry data, discussion with the HNC clinical team, and the electronic medical record (EMR) to identify patients who meet study inclusion criteria. Research staff will then review clinic rosters to identify eligible patients who are scheduled for an appointment in the Head and Neck Tumor Center. Study recruitment will be facilitated through the use of tested, structured protocols. [name] has evidenced-based strategies that have been successfully employed to recruit AA cancer patients to therapeutic trials. We will also use structured protocols from the principal investigator ([name]) and co-mentor [name], MPH. These protocols have been successfully employed and refined for clinic-based recruitment of patients with HNC to

participate in behavioral research during treatment periods. Recruitment is expected to be enhanced by the active clinical practice of the PI.

Prior to studying the NDURE intervention in a clinical trial, we will pre-test our intervention in n=3 patients to ensure proper implementation into clinical workflow. These patients will participate in the intervention and outcome assessment only for the purposes of pre-testing and assessing our implementation into clinical workflow but not for the purposes of analysis towards any of the study endpoints.

We propose to accrue 45 patients (white, n=30 and AA, n=15) to the study over 13 months. Based on data from MUSC/HCC for 2018, it is expected that 125 patients/year will be eligible for the study, of whom 28 (22%) are expected to be AA and 97 (78%) are expected to be white. Based on the PI and study team's prior experience recruiting and enrolling for similar studies embedded into clinical care, we anticipate that 50% of eligible patients will accrue to this study. Based on this 50% accrual rate, over the course of 13 months, we would expect to accrue 68 patients (n=15 AAs; n=53 white). Thus, by conservative estimates with appropriate over-sampling of AAs, our overall accrual target (n=45) and for the AA racial subgroup (n=15) appear highly feasible in the allocated 13 month accrual period.

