Because we plan to enroll consecutive patients for this clinic-based intervention, one potential concern relates to systematic, non-random differences between patients who participate in NDURE and patients who decline to participate. Enthusiastic, health-motivated patients may enroll while marginalized, burdened patients who distrust the medical system may preferentially decline. Alternatively, patients with few/no perceived barriers may disproportionately decline the intervention due to perceived lack of need while burdened patients participate because of the perceived need. Whichever, if any, situation occurs, our approach ensure that we will still be well positioned because we will collect information about which patients enroll/decline and their reasons for enrolling/declining to help refine NDURE for future dissemination.

Three strategies will be used to ensure retention of enrolled patients in the study. First, supportive and frequent interactions between the participant and navigator are expected to occur throughout NDURE, which should help mitigate against retention problems (for those in the NDURE arm). Second, we have accounted for the burden of surveys/questionnaires while patients are on treatment to ensure that the expected time commitment from surveys is reasonable and that the study interactions will be scheduled at a convenient time for patients (usually while at MUSC for clinical care already). Finally, remuneration will also occur on a schedule that is weighted towards providing the majority of the compensation at the end of the study time period.

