# Initiation of postoperative PORT > 6 weeks after surgery

We hypothesize that, compared to historical control data for patients undergoing surgery for HNC at MUSC followed by PORT between 2014-2016, patients who receive NDURE will have a decreased rate of PORT delays (initiation of PORT > 6 weeks after surgery).

Alternatively, our null hypothesis is that there will be no difference in the rate of PORT delay between patients who receive NDURE when compared to historical control data for patients undergoing surgery for HNC at MUSC followed by PORT between 2014-2016.

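### The overall historical comparison in Section 9.4.3 is not standardised or stratified by race, although the trial over-samples African American patients to one third of the cohort

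*Combined protocol and SAP*

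**What the plan says.** **Cohort.** Section 4.1 gives the target as "n=45; AA n=15; white n=30", so one third of patients are to be AA. Section 5.5 expects 125 eligible patients a year at the centre, "of whom 28 (22%) are expected to be AA and 97 (78%) are expected to be white". It calls the AA target feasible "by conservative estimates with appropriate over-sampling of AAs".

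**Comparators.** Section 9.1 describes the local control as "historical control data for patients undergoing surgery for HNC at MUSC followed by PORT between 2014-2016". The national control is described in the same way, from the National Cancer Database for 2006-2014. The race mix, size and confidence interval of either cohort are not given in this document; Section 9.4.3 refers to two cited publications.

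**Comparison.** Section 9.4.3 compares the rate of delay (PORT more than 6 weeks after surgery) with history by Fisher's exact test. If the upper 95% limit for NDURE lies at or below the lower 95% limit for the historical rate, a larger trial is considered warranted. No weighting, stratification or matching is stated. The covariates of Section 8.1 enter only the logistic model for unresolved barriers. Section 9.4.2 reports delay rates for white and AA patients separately, and Section 9.4.3 compares racial disparities with history and promises cautious interpretation.

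**Race and delay.** Section 2.2 states that AA patients are 31% more likely to be delayed, after adjustment for insurance, income, education and stage, and gives an overall delay rate of 56%.

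**The concern.** The overall delay rate is an average of the AA and white rates, weighted by their shares in the cohort. The trial sets those shares by design, and sets the AA share above that of the population the patients come from. If AA patients are delayed more often, as the plan states, an overall rate with one third AA is expected to be higher than the rate in a cohort with fewer AA patients, even if NDURE changes nothing. The difference from history then mixes the effect of navigation with the effect of over-sampling.

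The comparison carries weight. Section 4.2 justifies the single arm partly by well-defined historical controls and defines clinical impact relative to them. The interval rule in Section 9.4.3 informs whether a larger trial is warranted. An imbalance that the design itself creates, on a variable measured in every patient, can be removed in the analysis.

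**Working it through.** **The plan's own figures.** The 95% margin of error is 1.96 × √(p(1−p)/n). At p = 0.5 it is 0.146 for n = 45 (stated 0.15) and 0.253 for n = 15 (stated about 0.25). Expected accrual is 125 × 13/12 × 0.5 = 67.7 (stated 68), with 28 × 13/12 × 0.5 = 15.2 AA (stated 15) and 97 × 13/12 × 0.5 = 52.5 white (stated 53). All reproduce.

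**Race shares.** Trial: 15/45 = 33.3% AA. Eligible pool: 28/125 = 22.4%. The difference is 10.9 points. Filling 45 places at the pool's share would give about 0.224 × 45 = 10 AA patients, so the 15/30 split needs the over-sampling that Section 5.5 mentions. The same section also says "Because we plan to enroll consecutive patients for this clinic-based intervention"; the two statements need reconciling.

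**Formula.** With no NDURE effect, the race-mix shift is (trial AA share − historical AA share) × (AA delay rate − white delay rate).

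**Race-specific rates.** The plan does not say whether the 31% is a risk ratio or an odds ratio, so both are run. The overall rate is held at 56%, with historical AA share s.

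- Risk ratio: white rate = 0.56 / (1 + 0.31s). At s = 0.224 this is 0.524; AA = 1.31 × 0.524 = 0.686; gap 16.2 points.
- Odds ratio: the white rate is solved so that s × AA + (1 − s) × white = 0.56, with AA odds 1.31 times white odds. At s = 0.224: white 0.545, AA 0.611; gap 6.6 points.

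Both readings put AA delay above 60%, which agrees with the timely rate below 40% in Section 2.2.

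| Historical AA share (assumed) | Shift, odds-ratio reading | Shift, risk-ratio reading |
|---|---|---|
| 22.4% (2018 local pool) | +0.7 points | +1.8 points |
| 15% | +1.2 | +3.0 |
| 10% | +1.5 | +3.9 |
| 5% | +1.8 | +4.8 |

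For example, the first row is 0.109 × 6.6 = 0.7 and 0.109 × 16.2 = 1.8. With an overall rate of 45% instead of 56%, the first row becomes 0.7 to 1.4.

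**Size relative to precision.** At p = 0.56 and n = 45 the margin is 1.96 × √(0.56 × 0.44/45) = 0.145. The local shift is 5 to 12% of that, or 0.3 to 0.8 of a patient in 45. The national shift is 8 to 33%, or 0.5 to 2.2 patients.

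**Effect on the interval rule.** With exact (Clopper-Pearson) limits, a historical lower limit of 0.54 allows at most 17 delays in 45 (upper limit 0.535), and 0.56 allows 18 (0.557). A limit of 0.50 allows 15. These limits are assumed, since the plan gives none. A 2-point move therefore changes the threshold by one patient, and a 4-point move (0.50 to 0.54) by two.

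**Precision after reweighting.** The margin with AA weight w is 1.96 × √(w² × 0.25/15 + (1−w)² × 0.25/30). It is 0.150 at w = 0.224, 0.163 at 0.10 and 0.170 at 0.05, against 0.146 unweighted.

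**The case against.** The strongest case against acting has four parts.

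- **The historical mix is unknown.** The 22.4% is the expected 2018 eligible pool, not the 2014-2016 control. The 56% comes from the national study that Section 9.4.3 cites, and no local historical rate is given. The 31% is an adjusted effect used here to build a crude gap. This stands: the figures are conditional on stated assumptions.
- **The shift is small and conservative.** Locally it is less than one patient, and it makes NDURE look worse. This also stands. A reader might infer that over-sampling could produce a false signal of benefit; race mix works in the other direction.
- **Race-specific rates are already planned, and caution is promised.** This stands only in part. Separate rates are free of the race-mix shift, but the overall comparison and its interval rule still use the crude rate. Cautious wording does not remove a measured imbalance.
- **It is a pilot with a descriptive primary endpoint.** True, but the historical comparison is a listed secondary objective with stated hypotheses.

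A reader might also infer that the historical cohorts are shown to be broader in eligibility, since the trial has limits such as "Self-identified Hispanic ethnicity" as an exclusion and "No prior exposure to radiation therapy, with or without concurrent chemotherapy, for treatment of HNSCC" as a requirement, while Section 9.1 describes the controls in one line. The documents do not support that. A short description in a hypothesis statement is not a cohort definition, and the title of the cited local study refers to surgically treated squamous cell carcinoma. Where the plan does give shares, they are small: at the centre, 3% Hispanic and 1% other racial groups (Section 5.2). The size and direction of any wider eligibility effect cannot be determined.

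**Conclusion.** The point holds for race mix. The design raises the AA share to one third, the plan treats AA race as a predictor of delay, and the overall comparison in Section 9.4.3 makes no allowance for it. The resulting bias is about 0.7 to 1.8 points against NDURE if the local control had the 2018 AA share and 56% delay. It is about 1 to 5 points if the national AA share was 5 to 15%. Both AA shares are assumptions. The bias is systematic but well inside the roughly 15-point margin, and would alter the interval rule only in a borderline result. It does not invalidate the comparison or undermine the primary estimate. This is a cheap improvement.

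**What to change.** In Section 9.4.3, make the overall historical comparison race-standardised. Either weight the historical AA and white rates 1/3 and 2/3 (or by the shares actually enrolled), or reweight the NDURE rate to the historical mix. Replace the crude Fisher test with a race-stratified exact or Mantel-Haenszel test, and apply the interval rule to the standardised rates. State the race mix of each control cohort. Where record-level data are available, add a sensitivity analysis restricted to historical patients who meet the trial's eligibility criteria.

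**Cost.** No new patients are needed, and the disparity comparison already planned in Section 9.4.3 requires race-specific historical rates. Reweighting NDURE widens its margin from 0.146 to 0.150 at 22.4% AA, and to about 0.16 to 0.17 at an assumed 10 to 5% AA. Weighting the historical rates instead leaves the NDURE interval unchanged; the change in the historical interval cannot be computed without the cohort sizes. The eligibility restriction needs record-level access, which the documents do not confirm, and would shrink the historical sample.

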# Initiation of postoperative PORT > 6 weeks after surgery

We hypothesize that, compared to historical control data for patients undergoing surgery for HNC followed by PORT in the National Cancer Database between 2006-2014, patients who receive NDURE will have a decreased rate of PORT delays (initiation of PORT > 6 weeks after surgery).

Alternatively, our null hypothesis is that there will be no difference in the rate of PORT delay between patients who receive NDURE when compared to historical control data for patients undergoing surgery for HNC followed by PORT in the National Cancer Database between 2006-2014.

# 9.2 SAMPLE SIZE DETERMINATION

Because this is a pilot study generating preliminary data, our singlearm trial is not powered to detect a pre-specified improvement (i.e. reduction) in the rate of delayed PORT with NDURE. Rather, we

Figure 1. Margin of Error Rates of Delayed PORT. Margin of error for rates of delayed PORT for overall cohort and white and African American subgroups in the single-arm NDURE pilot study.

justify our sample size based on the desired precision (as measured by the half-width of a 95% CI, also known as the margin of error) in estimates of PORT delay rates. Fig. 1 shows the margin of error for proportions ranging from 0 to 0.5 for n=15, 30 and 45 the sample sizes for AA and white patient subgroups and the entire cohort, respectively. Because the margin of error for proportion p is equivalent to that for proportion 1 - p, we limit Figure 1 to proportions ranging from 0 to 0.5.) For PORT delay rate estimates based on the entire sample, the maximum margin of error (smallest precision) is 0.15 occurring for a proportion of 0.5, with the margin of error decreasing (precision increasing) for proportions closer to 0 or 1. For example, the 95% CI for an observed PORT delay rate of 50% is 35% to 65%, indicating an acceptable level of uncertainty in the estimate and providing adequate precision to allow accurate design of a randomized trial evaluating the NDURE intervention. The margin of error is greatest for the subpopulation of AA patients because of the smaller sample size. Nonetheless, the maximum margin of error at an observed proportion of 50% is approximately 0.25 (95% CI = 25% to 75%) which is sufficient information to adequately design a randomized study to evaluate the efficacy of NDURE in these subpopulations. We considered extending the study accrual to increase enrollment to targets of 75 patients (white, n=50 and AA, n=25). The maximum margin of error for a proportion of 0.5 would decrease to 0.11 (relative to 0.15 with enrollment targets of n=45), which is a negligible improvement. The 95% CI for an observed PORT delay rate of 50% in the larger (n=75) cohort would be 39% to 61% (relative to 35% to 65% in the n=45 cohort), which again does not significantly improve precision in terms of accurate design of a randomized trial evaluating the NDURE intervention. The AA sub-population has the greatest margin of error because of the smaller sample size. By increasing enrollment from n=15 AAs to n=25 AAs, the margin of error would only decrease from 0.25 (95% CI = 25% to 75%) to 0.20 (95% CI = 30% to 70%) at an observed proportion of 50%, which again does not significantly improve the ability to design a randomized study to evaluate the efficacy of NDURE in these subpopulations. Given the volume of eligible patients at MUSC and historical participation rates, we consider n=45 (AA n=15; white n=30) subjects to be a reasonable sample size target for patients who enroll and complete the study. This approach and data analysis plan recognizes that early phase trials do not produce definitive clinical conclusions, but provide information to ascertain whether additional large-scale clinical trials assessing efficacy are warranted and estimates of precision to inform future study design.

Every effort will be made to minimize missing data and lost-to-follow-up participants. Participants will complete assessments at baseline and post intervention using an iPad-based REDCap collection method. The program coordinator will attempt to contact patients at least three times using a variety of methods of communication (e.g. text message, phone call, email, mail, etc) to complete outcome measures. This method resulted in 100% instrument completion in prior studies conducted by our team. Patients in the ITT population for whom the primary endpoint is not evaluable due to loss to follow-up will be considered NDURE failures, and their time to PORT will be treated as exceeding 6 weeks for the purposes of analysis (a very conservative approach for this single-arm, phase II pilot study. In the event that missing data occur for other endpoints, we will address them via standard multiple imputation procedures. In general, less than 10% missing data has little impact on study power and does not induce bias regardless of the missing data mechanism. If missing data is greater than 10%, it will be imputed using Markov Chain Monte Carlo (MCMC) methods. The data augmentation will be applied to Bayesian inference with missing data by repeating imputation step (i.e., simulating the missing values based on the observation) and step for exploring the posterior distribution based on the complete sample estimates obtained from the imputation step.

Our plan to accrue 45 patients (white, n=30 and AA, n=15) to the study over 13 months is highly feasible. Based on data from MUSC/HCC for 2018, it is expected that 125 patients/year will be eligible for the study, of whom 28 (22%) are expected to be AA and 97 (78%) are expected to be white. Based on the PI and study team's prior experience recruiting and enrolling for similar studies embedded into clinical care, we anticipate that 50% of eligible patients will accrue to this study. Based on this 50% accrual rate, over the course of 13 months, we would expect to accrue 68 patients (n=15 AAs; n=53 white). Thus, by conservative estimates with appropriate over-sampling of AAs, our overall accrual target (n=45) and for the AA racial subgroup (n=15) appear highly feasible in the allocated 13 month accrual period.

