As such, patients who meet study inclusion criteria but subsequently develop exclusion criteria #4 or #5 during the course of the study will be replaced since the primary endpoint is anchored to findings that occur after analysis of the pathologic specimen obtained during surgery. Patients in the modified ITT population for whom the primary endpoint is not evaluable due to loss to follow-up will be considered navigation failures, and their time to PORT will be treated as exceeding 6 weeks for the purposes of analysis.

We will also perform an efficacy analysis on the per-protocol analytic dataset, a subset of the modified ITT population who completed all 3 NDURE study sessions. These patients are judged to have complied with the protocol sufficiently to ensure that these data would be likely to represent the effects of the NDURE intervention according to the underlying scientific model.

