# 9.4 STATISTICAL ANALYSES

# 9.4.1 GENERAL APPROACH

We will construct graphical displays and calculate descriptive statistics (e.g. frequencies and percent for categorical variables, and mean, median, standard deviation, and range for continuous variables). Covariates will be specified below. For inferential tests, we will use a p-value of 0.05, two-sided, and 95% confidence intervals (CIs) to assess statistical significance (Type I error). Normality of the data will be assessed before underlying statistical procedures will be performed. We will evaluate variable transformations as needed to satisfy assumptions and consider transformations of variables to induce approximate normality and stabilize variance as needed. Nonparametric tests will be applied when appropriate.

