Secondary endpoints for feasibility, acceptability, fidelity and HNC care delivery will be analyzed as follows. For study accrual, we will calculate the proportion and frequency of eligible patients who accrue (overall, white, and AA). Given its pilot nature, the study is not designed to evaluate racial differences in accrual, although reasons for study decline will be collected, analyzed by race, and used to refine recruitment. NDURE completion will be analyzed as 1) the percentage of enrolled patients who attend all three in-person NDURE sessions and 2) the proportion of three in-person NDURE sessions that are completed. For navigator caseload, we will consider the frequency of simultaneous cases navigated. Navigator time allocation for direct and indirect time, as well as patient-report measures of satisfaction with navigation (acceptability) will be summarized as described above for continuous data. NDURE fidelity will be analyzed as the proportion of enrolled patients who have a BRP documented in the EMR. For HNC care delivery processes, we will calculate the proportion of patients receiving each key HNC care delivery process.

For secondary endpoints evaluating the theoretical constructs underlying NDURE (care coordination, support, perceived susceptibility, severity, barriers, and self-efficacy), we will estimate the mean change in each measure (pre-post) as well as standard deviations and 95% CIs for each; comparisons will be conducted using Wilcoxon sign-rank test. Baseline levels of each dependent variable will be controlled in each model; additional covariates will be considered by examining associations between potential covariates and each dependent variable using linear regression (p < .10 where the change in each outcome measure is the dependent variable). This method will allow estimation of intervention effects while adjusting for potential confounders.

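### Section 9.2 wrongly says that under 10% missing data cannot cause bias whatever the mechanism, and its 10% imputation trigger does not fit its promise of multiple imputation for any missing non-primary endpoint

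*Combined protocol and SAP*

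**What the plan says.** The missing-data rules are in Section 9.2. The primary endpoint is dealt with separately: a patient lost to follow-up is counted as having started PORT late. Section 9.3 repeats this for the analysis population: "Patients in the modified ITT population for whom the primary endpoint is not evaluable due to loss to follow-up will be considered navigation failures".

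Three consecutive sentences then cover everything else. The first sets no threshold: "In the event that missing data occur for other endpoints, we will address them via standard multiple imputation procedures". The second, introduced as a generality, says that "less than 10% missing data has little impact on study power and does not induce bias regardless of the missing data mechanism". The third reads: "If missing data is greater than 10%, it will be imputed using Markov Chain Monte Carlo (MCMC) methods". A last sentence outlines data augmentation.

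The planned size is "n=45 (AA n=15; white n=30) subjects to be a reasonable sample size target for patients who enroll and complete the study". For the health-behaviour scores, Section 9.4.3 says "we will estimate the mean change in each measure (pre-post) as well as standard deviations and 95% CIs for each". Satisfaction scores are summarised as continuous data and care processes as proportions. No sensitivity analysis for informative missingness is planned for any of these endpoints.

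**The concern.** There are two faults in adjoining sentences. The first is a false statistical claim. No missing fraction short of zero guarantees an unbiased result under every mechanism, and nothing in the documents limits the claim to data missing completely at random or at random.

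The second is that the handling rule is unclear. One sentence calls for imputation whenever data are missing, while the next two suggest that it starts above 10%. Two analysts could follow the same paragraph and report different results.

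The documents themselves give a reason to expect informative non-response. Section 5.5 accepts that treatment toxicity and competing demands may lead patients to refuse surveys or withdraw. In the visit table under Flow Diagram, both satisfaction scales, the care-transition measure and every post-intervention construct score are collected at Visit 5. Patients with the hardest course could therefore be the ones without scores. Section 4.2 says that the trial exists to supply estimates and precision for a larger trial, so bias in those estimates matters even in a pilot.

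**Working it through.** **Inputs.** From Section 9.2: 45 patients (15 AA, 30 white) and the 10% threshold. From Section 9.4.1: 95% confidence intervals. The documents do not say how far missing patients differ from observed ones. I call that difference d, in SD units, and show a range.

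**The plan's own figures.** The 10% statement has no derivation to reproduce. The only numerical design basis is the half-width 1.96 × √(0.25/n):

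- n = 45: 0.146 (stated 0.15)
- n = 15: 0.253 (stated 0.25)
- n = 75: 0.113 (stated 0.11)
- n = 25: 0.196 (stated 0.20)

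These all agree.

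**Largest count below 10%.** Whole cohort: 4/45 = 8.9% (5/45 = 11.1%). White patients: 2/30 = 6.7%. AA patients: 1/15 = 6.7%. Exactly 10%, such as 3/30, falls under neither sentence. The plan does not say whether the percentage is counted per variable, per patient or per subgroup: 2/15 = 13.3% in AA patients exceeds the trigger even if the whole cohort does not.

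**Scores, 4 of 45 missing and not imputed.**

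- Bias = (4/45) × d = 0.0889d
- SE = 1/√41 = 0.156 SD
- Coverage = Φ(1.96 − bias/SE) − Φ(−1.96 − bias/SE)

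| Assumed d (SD) | Bias (SD) | Bias/SE | Coverage of nominal 95% CI |
|---|---|---|---|
| 0 | 0 | 0 | 95.0% |
| 0.5 | 0.044 | 0.28 | 94.1% |
| 1 | 0.089 | 0.57 | 91.2% |
| 1.5 | 0.133 | 0.85 | 86.3% |
| 2 | 0.178 | 1.14 | 79.3% |

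Bias vanishes only at d = 0, which is a condition on the mechanism.

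**Proportions, as bounds.** Suppose a care process is met in 33 of 41 observed patients, or 80.5%. If all four missing patients failed it, the full-cohort value is 33/45 = 73.3%, so the complete-case figure is 7.2 points too high. If all four met it, the value is 37/45 = 82.2%, and the figure is 1.7 points too low. These are extremes, not expected values.

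**The sentences side by side at 4/45 missing.** The first requires multiple imputation. The second says that there is nothing to correct. The third does not apply. MCMC is itself a standard way to carry out multiple imputation, so the first and third sentences may describe the same procedure with and without a threshold.

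**The case against.** The strongest reply is that the paragraph can be read consistently: multiple imputation always, with MCMC as the technique above 10%. This stands as a possible reading. A reader might infer that the plan prescribes complete-case analysis below 10%. The text never says so; that is an inference, though a natural one, because the no-bias sentence has no purpose under the consistent reading.

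The second reply concerns scope. A reader might infer that all care-process endpoints are exposed as much as the surveys. The documents do not support that. Section 8.1 defines these measures by events such as a report issued, a referral placed or a consultation attended, and Table 1 describes EMR tracking of care delivery. Gaps are most plausible where referral, consultation or radiation takes place outside MUSC.

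The third is likelihood. Section 9.2 plans at least three contact attempts by several routes and reports complete instruments in the team's earlier studies, and Section 5.5 expects good retention. The rule may seldom come into play. That lowers the expected harm but does not make the sentence true.

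The fourth is size. At d = 0.5 SD coverage is still about 94%. At 1 SD the bias of 0.089 SD compares with an interval half-width of 1.96 × 0.156 = 0.31 SD. The "trial is not powered to detect a pre-specified improvement (i.e. reduction) in the rate of delayed PORT with NDURE", and these endpoints are largely descriptive. All of this stands and keeps the point modest.

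**Conclusion.** The claim of no bias regardless of mechanism is wrong as written, and the 10% trigger is inconsistent with, or at best obscures, the unconditional promise of multiple imputation before it.

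The consequence is confined to secondary endpoints, mainly the patient-reported scores. A reader might go further and infer that the main result is at risk. The documents do not support that: the primary endpoint has its own rule for loss to follow-up, and the criterion in Section 9.4.3 for further testing uses PORT delay and its racial disparity, not these scores.

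The effect is negligible if missing patients differ by half an SD or less. It becomes material at 1 to 2 SD, where coverage falls to about 91% and 79%. These figures assume 4 of 45 missing, no imputation, a normal approximation and a value of d that the documents do not give.

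**What to change.** Delete the no-bias sentence and the 10% trigger, and keep one rule: multiple imputation for any missing secondary endpoint, whatever the amount, under a stated missing-at-random assumption.

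Name the imputation variables: race, sessions attended, symptom severity and PORT-delay status. Symptom severity is scheduled at every visit from Visit 1, so an earlier value should exist when Visit 5 is missed. PORT-delay status is assigned rather than observed for patients lost to follow-up, and the plan should say which value enters the model. Add the baseline score only for scales measured at Visit 1. The two satisfaction scales and CTM-15 are collected only at Visit 5 and have none.

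Add one not-at-random sensitivity check: shift the imputed scores over a stated range, for example 0.5 and 1 SD, and count missing process measures as not met. Edentulous patients, whom Section 8.1 defines as not evaluable for dental extractions, are not missing data. The check is needed because imputation under missing at random removes only what the named variables explain. It does not by itself remove the not-at-random bias shown above, and the shift check displays that sensitivity rather than correcting it.

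The cost is a change of wording in the plan and modest extra analysis work. No additional patients or data collection are needed.
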